**C.2.d. Statistical Methods.** The hypotheses associated with Aim 1 are interested in the effect of oxytocin on cocaine craving and stress in response to the TSST. It is hypothesized that cocaine-dependent participants receiving oxytocin will demonstrate greater attenuation of stress and craving response to TSST as compared to those receiving matched placebo. A linear mixed effects model containing all serially measured time points will be used to assess the effects of oxytocin versus placebo on each dependent variable. Restricted maximum likelihood (REML; Patterson and Thompson, 1971) methods will be used to estimate the fixed effects and variance components, and baseline values will be used as covariates in the regression models. To test the hypothesis that women will experience greater ameliorative effects of oxytocin on stress and craving response following the TSST as compared to males, similar models will examine the differential (interaction) in the scores reported between men and women by treatment group (oxytocin vs. placebo). Additionally, as an exploratory analysis, the strength of the effects of oxytocin in women will be assessed with differences in estrogen and menstrual cycle phase as independent variables. In a subgroup analysis of women entered into the study, linear mixed effects models will be developed to assess the association of estrogen and menstrual phase (independently) on the stress and craving response to the TSST. Non-linear associations will also be explored using cubic spline models (Marrie et al., 2009). Within each family of dependent measures, the Type I error rate will be controlled using a post-hoc Bonferroni correction.

The hypotheses associated with Aim 2 are concerned with the impact of oxytocin on cocaine cue reactivity. It is hypothesized that oxytocin will decrease cue-induced cocaine craving in cocaine-dependent men and women compared with placebo administration. Post-acquisition preprocessing and statistical analysis will be performed using Matlab 7.8 (Mathworks, Sherborn, MA) with Statistical Parametric Mapping software 8

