**C.2.e. Power and Sample Size.** *Aim 1.* It is hypothesized that oxytocin will decrease ratings of subjective stress and cocaine craving following the TSST relative to placebo. Pilot data suggests an expected between group mean differences in total cocaine craving (CCQ) following the TSST of  $\Delta = 8.24$  with a RMSE = 11.03 ( $d = 0.75$ ) (Cohen, 1988) and a stress rating (VAS) difference of  $\Delta = 1.07$  with a RMSE = 2.20 ( $d = 0.49$ ). As in the oxytocin pilot study, participants will be assessed at four post TSST time points ( $m$ ), with an anticipated intraclass correlation coefficient of 0.78 for both craving and stress outcomes (ICC = 0.78 & 0.79, respectively). The design effect, which accounts for the multiple correlated observation within each subject, is estimated to be 3.35 (DE =  $[1 + (4-1)0.78]$ ) (Donner and Klar, 2000). Assuming independent observations and an effect similar to the pilot data for the stress response ( $d = 0.48$ ), the total effective sample size would be 140 subjects (35 men and 35 women per treatment arm) to provide 80% power with a type I error rate of 0.05. In a clustered setting, the sample size is  $N_{\text{effective}} = nm/DE$  where  $n$  is the number of participants required when  $m$  replications within participants are performed after accounting for the design effect (DE). For the study at hand, the total

Version 16.0 (Revised 08/01/2016)

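### Aim 1 uses plain Bonferroni within families; Holm's step-down gives the same family-wise control and never less power, but how much it gains depends on family membership, which the plan does not list

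*Combined protocol and SAP*

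**What the plan says.** The Aim 1 paragraph of section C.2.d (Statistical Methods) ends with the only multiplicity rule for the stress-task outcomes: "Within each family of dependent measures, the Type I error rate will be controlled using a post-hoc Bonferroni correction". No step-down procedure is mentioned anywhere. The plan does not say which measures make up a family, how many there are, or whether craving and stress share one. The assessment text in C.2.c.2 offers several candidates: the CCQ-Brief, items of the Within Session Rating Scale, the STAI, cortisol, heart rate and blood pressure. Section 5.1 names craving and stress response together as the primary outcome.

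Section C.2.e sizes the trial on the weaker outcome, stress, at d = 0.48. It states that "the total effective sample size would be 140 subjects (35 men and 35 women per treatment arm") are needed "to provide 80% power with a type I error rate of 0.05". It notes that "participants will be assessed at four post TSST time points", with an ICC of 0.78, and arrives at 120 completers. The stated power is 80% for stress and 98% for craving (d = 0.75). Both figures are at an alpha not divided among measures.

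**The concern.** Bonferroni tests every member of a family of k measures at 0.05/k. Holm starts at the same level for the smallest p-value but relaxes it after each rejection, to 0.05/(k − 1), then 0.05/(k − 2), and so on, stopping at the first failure. The two give the same guarantee on family-wise error, and for the tests themselves Bonferroni is never the more powerful.

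The pattern of planned effects makes this worth attention. Craving is expected to be strong and stress weaker, and stress is the outcome that drives the sample size. If the two share a family, craving would usually be rejected first and stress would then be tested at a larger alpha. Under Bonferroni, a real stress effect with a p-value between 0.025 and 0.05 would be declared non-significant even though craving had already been rejected.

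**Working it through.** **Holm is never worse.** Suppose Bonferroni rejects a measure, so its p-value is at most 0.05/k. Every smaller p-value is then also at most 0.05/k, and every Holm threshold is at least 0.05/k, so Holm reaches and rejects that measure. For the error rate, let m of the k hypotheses be true. When Holm rejects its first true null, the threshold in force is at most 0.05/m. By the union bound the chance of any false rejection is at most m × 0.05/m = 0.05, whatever the dependence.

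**The plan's own figures.** Sidedness is not stated; two-sided reproduces the plan. At 70 effective participants per arm the non-centrality for stress is 0.48 × √(70/2) = 2.840, and power is Φ(2.840 − 1.960) = 81.1% (80.5% with a t-test), against the stated 80%. For craving it is 99.3%, against 98%. The conversion 140 × 3.35/4 = 117.25 gives 118, rounded to 120. The plan therefore reproduces at an undivided 0.05.

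**Inputs for the comparison.** 120 completers, m = 4 and ICC 0.78 (C.2.e) give a design effect of 1 + 3 × 0.78 = 3.34 and an effective N of 120 × 4/3.34 = 143.7. The non-centrality is d × √(143.7/4): 2.877 for d = 0.48 and 4.496 for d = 0.75. Assumptions not in the documents are two-sided tests, the family membership, a correlation of 0.5 between measures, and the pilot effects taken as true.

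**Stress power by formula**
- Undivided 0.05: Φ(2.877 − 1.960) = 82.0%
- Bonferroni, k = 2: Φ(2.877 − 2.241) = 73.8%
- Bonferroni, k = 3: Φ(2.877 − 2.394) = 68.6%
- Bonferroni, k = 4: Φ(2.877 − 2.498) = 64.8%
- Craving at 0.025: Φ(4.496 − 2.241) = 98.8%, which is why it would nearly always go first if its pilot effect is real

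**Stress power by simulation** (correlated normal test statistics, at least 200,000 draws per family, correlation 0.5):

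| Assumed family (d) | Bonferroni | Holm |
|---|---|---|
| Craving 0.75, stress 0.48 | 74% | 82% |
| Craving 0.75, two stress measures at 0.48 | 69% | 79% |
| Two measures at 0.75, two at 0.48 | 65% | 79% |
| Two stress measures at 0.48 | 74% | 79% |
| Craving 0.75, stress 0.48, one null | 69% | 74% |
| Craving 0.75, stress 0.48, two nulls | 65% | 69% |
| Stress 0.48, one measure at 0.3 | 74% | 75% |
| Stress 0.48, three measures at 0.3 | 65% | 67% |
| Stress 0.48, one null | 74% | 74% (gain of 0.1 to 0.2 points) |

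No draw showed Bonferroni rejecting a measure that Holm retained. The craving-and-stress result barely depends on the correlation: at 70 effective per arm, Holm gives about 81.0% for correlations from 0 to 0.9.

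**Share of the loss recovered.** For craving and stress alone it is nearly all. For craving, stress and two nulls it is (68.6 − 64.8)/(82.0 − 64.8) = 3.8/17.2, or about 22%. With one null partner it is about 2%.

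**The case against.** The strongest case against the point is that its most attractive figure, 74% to 82%, rests on a family the documents never define. C.2.d speaks of families in the plural, and C.2.e powers craving and stress separately. If families are formed by construct, craving releases no alpha to stress. If a construct has a single measure, there is no penalty to recover. If they follow the assessment headings, the self-report family has seven or more members: the CCQ-Brief, the STAI and at least five rating-scale items. The term post-hoc might also refer to follow-up contrasts within a model. In addition, craving goes first only if its pilot effect is real, and the one placebo-controlled oxytocin pilot described (C.1.b) had 16 marijuana-dependent participants. If the true craving effect were 0.3, stress power would move only from about 74% to 75%. All of this stands, and it limits the size of the gain.

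It is also true that Bonferroni is valid, that section 5.9 says this is not an intervention trial, and that Bonferroni has simple matching simultaneous intervals. The validity is not in dispute. The intervals would be a reason to keep Bonferroni only if the plan used them, and it promises none.

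None of these arguments reverses the direction. Holm is at least as powerful in every family, and the same holds for follow-up contrasts.

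A reader might infer that Holm generally wins back most of the stress power lost to Bonferroni. The documents do not support that: it is true for stress paired with strong companions and false for weak or null ones.

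**Conclusion.** The point holds as an efficiency improvement. Holm gives the same family-wise control as the planned correction and never rejects fewer hypotheses. Depending on the family, the gain in stress power runs from essentially none (one null partner) through about 4 to 5 points (craving, stress and one or two nulls; two stress measures) to about 8 points (craving and stress alone). It is larger still if several strong measures share the family. These figures rest on two-sided tests, the pilot effects taken as true, the plan's design-effect model and a correlation of 0.5. The existence and direction of the advantage rest on none of them.

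A reader might also infer that the plan's Type I control is faulty; it is not. Nor does Holm by itself secure the stated 80% power for stress. In the table, that level is reached only for the craving-and-stress pair, because the sample size was set at an undivided 0.05. That, and the undefined families, are separate gaps. The direct benefit is clearest in the two-member case: holding 80% stress power under Bonferroni would need 83 effective per arm, that is 2 × 83 × 3.35/4 = 139.0, or about 140 completers. At 80% retention this is 139.0/0.8, or about 174 recruited instead of 152. Holm needs none of those extra participants.

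**What to change.** In C.2.d, replace the Bonferroni sentence with one such as: 'Family-wise Type I error will be held at 0.05 by Holm's step-down procedure within each of the families listed below.' Beside it, list the members of every family before unblinding, and say whether craving and stress belong together. Without that list neither procedure can be applied reproducibly and the gain cannot be stated. Report Holm-adjusted p-values with unadjusted 95% confidence intervals, labelled as unadjusted.

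The cost is one sentence and a short list, with no new data and no extra participants. The one real drawback is that Holm has no simple matching simultaneous confidence intervals, so an interval and its adjusted p-value may occasionally appear to disagree.

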Presentation of cocaine-paired cues elicits a stress response in cocaine-dependent individuals. Neuroimaging studies indicate substantial overlap in the corticostriatal limbic circuitry responsible for cue and stress-primed drug craving. Oxytocin receptors have been localized to these same regions and preclinical studies have shown that oxytocin attenuates the acute reinforcing properties of psychostimulants. Despite these findings, little is known about the role of oxytocin in modulating the affective response to cocaine-paired cues and associated neural activity in cocaine-dependent men and women and whether there are gender differences in this modulation.

**Hypothesis 2a:** Intranasal administration of oxytocin will decrease subjective ratings of cue-induced cocaine craving in cocaine-dependent men and women compared to placebo administration.

**Hypothesis 2b:** Intranasal administration of oxytocin will decrease functional activity in the anterior cingulate cortex, amygdala, striatum, and prefrontal cortex compared to placebo administration.

**Exploratory Hypothesis 2c:** The attenuation of functional activity in the anterior cingulate cortex, amygdala, striatum and prefrontal cortex following oxytocin administration will be greater in cocaine-dependent women as compared to cocaine-dependent men.

**Exploratory Hypothesis 2d:** Oxytocin will modulate resting-state and task-related functional connectivity among sub-networks implicated in reward and motivation (nucleus accumbens, and orbitofrontal cortex),

memory and learning (amygdala and hippocampus), and cognitive control (prefrontal cortex and anterior cingulate cortex). Oxytocin may increase connectivity between reward/motivation and cognitive control sub-networks in craving states as an index of top-down regulation.

**In summary**, the proposed project will provide important data on the effect of oxytocin on stress and craving in cocaine-dependent individuals, explore the neural circuitry involved in response to oxytocin administration, and investigate whether sex/gender differences in response exist.

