Significant sexual dimorphism in frontal-limbic-striatal structure, function, and neurochemistry are well documented (Cahill, 2006). Therefore, it is not surprising that there are sex differences in the neural correlates of drug craving. For example, stressful imagery produced greater activity in the left anterior and right posterior cingulate, left insula, and inferior medial cortices of cocaine-dependent women as compared to cocaine-dependent men (Li et al., 2005). On the other hand, cocaine-dependent women exposed to guided imagery of cocaine use exhibited significantly less activity in the amygdala, insula, orbitofrontal and ventral cingulate cortices as compared to cocaine-dependent men (Kilts et al., 2004).

Interestingly, oxytocin receptors appear to be widely distributed within frontal-striatal-limbic regions. *In situ* hybridization studies have localized oxytocin receptor mRNA in the hypothalamus, rostral regions of the frontal cortex, bed nucleus of the stria terminalis, anterior cingulate, dorsal striatum, and the amygdala (Yoshimura et al., 1996; Yoshimura et al., 1993). In addition, oxytocin administration attenuates amygdala activity to emotional evocative faces (Domes et al., 2007). Of note, the reduction in amygdala activity was observed in response to both aversive and happy faces, indicating that oxytocin may attenuate reactivity to both aversive and appetitive stimuli.

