(SPM 8, The Wellcome Department of Cognitive Neurology, London). All volumes within a task run will be realigned to the first volume. After realignment (including adjustment for sampling errors), scans with greater than one mm in three axes or one degree in three orientations will be excluded from group analyses. Following realignment, images will be stereotactically normalized into a standard space with a resolution of 2x2x2 mm voxels using the Montreal Neurological Institute (MNI) EPI template in SPM8. Subsequently, the data will be smoothed with a 8x8x8 mm Gaussian kernel and will be high-pass filtered (cue exposure paradigm cut-off period = 288s). Following preprocessing, within-task data from individual participants will be analyzed with a fixed-effects general linear model (GLM), with cocaine cue exposure activity modeled as a box-car function convolved with the standard canonical hemodynamic response function. The GLM procedure is repeated for each voxel with six movement parameters (3 rotation values in radian and 3 translation values in millimeter) included as covariates to control for the influence of head motion on the data. First-level analysis will be conducted and contrast maps will be generated. For the cue exposure paradigm, the main contrast of interest is the cocaine pictures vs. neutral objects contrast. Following first-level analysis, subject-specific contrasts will be entered into second-level, random-effects analyses. Areas of brain associated with group (oxytocin vs. placebo) and sex (women vs. men) differences on these contrasts will be identified using independent samples t-tests within a GLM framework. The combined group parameter maps will be threshold using a significance level of  $p < 0.05$ , corrected for multiple comparisons.

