For Exploratory Hypothesis 2d, a graph-theory approach to functional connectivity will be used. The BCT (Rubinov & [name], 2011) includes metrics specifically designed for functional brain networks, which are fully connected with weighted and signed connections. The metrics combine both positive and negative weights, but weight the positive connections more heavily. Within each of 116 anatomical regions of the AAL atlas, the average intensity value at each time point will be extracted for each subject. The time series (shifted by one TR) will be segmented into four separate time series, one for each condition (cocaine images, blur, objects, rest) (Fair et al., 2007; Just et al., 2004). Correlation matrices will then be computed for each subject and each condition and submitted to the BCT. For each subject and each condition, several BCT metrics will be computed (see Rubinov & [name], 2011 for more details). Network measures include *modularity* and *number of modules*. Node-specific measures include *diversity coefficient*, *within-module weights*, *within-module clustering coefficient*, and *strength*. We will also compute 20 random networks for each subject that preserve the weight and strength properties of the cocaine network (following Rubinov & [name], 2011), since that is the network of most interest. The same metrics that are computed for the cocaine, object, blur, and rest networks will be computed for the 20 random networks, then averaged to provide a single metric for the random network. In addition, a group-average correlation matrix will be computed (Pearson r-values from individual participants are Fisher z-transformed prior to averaging) for each of the four conditions and subject groups to obtain a modularity partition for the group, which will be visualized using Gephi software (Bastian, Heymann, & Jacomy, 2009), as in Figure 4. Network and node-based metrics will be submitted to mixed ANOVAs (one ANOVA for each metric and each node in the case of node-based metrics) with gender and treatment as between-subjects variables and condition (cocaine, object, blur, rest, random) as the repeated factor. Most metrics allow for comparison with the random networks except for strength and weight metrics because those are preserved in random networks and will be identical to the cocaine condition.

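### Exploratory Hypothesis 2c is a sex-by-oxytocin interaction, but the activation analysis names only a drug difference and a sex difference, so 2c is not tested as written

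*Combined protocol and SAP*

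**What the plan says.** Under Specific Aim 2, the subject of Exploratory Hypothesis 2c is "The attenuation of functional activity in the anterior cingulate cortex, amygdala, striatum and prefrontal cortex". The prediction is that this reduction "following oxytocin administration will be greater in cocaine-dependent women as compared to cocaine-dependent men".

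The only analysis of activation maps is in C.2.d, Statistical Methods (Aim 2 part). At the first level, "the main contrast of interest is the cocaine pictures vs. neutral objects contrast". Those per-person contrasts go into a second-level random-effects analysis. Its targets are "Areas of brain associated with group (oxytocin vs. placebo) and sex (women vs. men) differences on these contrasts". As to method, the plan states that they "will be identified using independent samples t-tests within a GLM framework". Nothing there names a sex-by-drug term, a difference-of-differences contrast, or a sex comparison of oxytocin-minus-placebo maps.

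Two other parts of C.2.d do combine sex and drug, but for other outcomes:
- For the Aim 1 stress-task scores, "similar models will examine the differential (interaction) in the scores reported between men and women by treatment group (oxytocin vs. placebo".
- For the connectivity metrics of Hypothesis 2d, mixed ANOVAs are planned "with gender and treatment as between-subjects variables and condition (cocaine, object, blur, rest, random) as the repeated factor".

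C.2.c.2 (fMRI Sessions) states that each participant is scanned twice, once after oxytocin and once after placebo, in counterbalanced order.

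**The concern.** A claim that the drug works better in one sex is a claim about an interaction. The women-versus-men test on cocaine-minus-neutral maps asks something else: whether the sexes differ in cue reactivity, whatever they were given.

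The protocol's own background says such differences already exist. In A. Significance it reports that "cocaine-dependent women exposed to guided imagery of cocaine use exhibited significantly less activity in the amygdala, insula, orbitofrontal and ventral cingulate cortices" compared with men. Those regions overlap the ones named in 2c, and lower activity in women is also the direction that greater attenuation would produce. If the sex map were read as the answer to 2c, a sex difference unrelated to oxytocin could pass for a sex difference in oxytocin response. Conversely, a real differential effect enters the sex test at only half its size and can be offset by a placebo gap in the other direction.

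**Working it through.** **Sample size in the plan.** The documents give no power for 2c. The imaging sample is inherited from Aim 1 (C.2.e): 140 × 3.35 / 4 = 117.25, taken up to 118 and then rounded to 120 completers. This reproduces. C.2.e gives 60 completers per group for imaging; I use 60 women and 60 men.

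**What each test estimates.** Let W and M be the mean cocaine-minus-neutral response in women and men, with subscripts O (oxytocin) and P (placebo). Over the cells (W_O, W_P, M_O, M_P) the contrast weights are:

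| Test | Weights |
|---|---|
| Drug (planned) | ½, −½, ½, −½ |
| Sex (planned) | ½, ½, −½, −½ |
| Interaction (2c) | 1, −1, −1, 1 |

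Drug × interaction: ½ + ½ − ½ − ½ = 0. Sex × interaction: ½ − ½ + ½ − ½ = 0. Both planned contrasts are therefore orthogonal to the one that 2c needs. Rearranged,

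sex contrast = (W_P − M_P) + ½ × interaction.

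The sex test is the placebo gap plus half the interaction, and it cannot separate the two.

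**Size, under assumptions.** None of the following is in the documents: a within-person correlation ρ of 0.5 (range 0.3 to 0.78), the effect sizes below in single-scan SD units, and an uncorrected two-sided 5% level.

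- SE(sex, mean of two maps) = √[2 × (1 + ρ)/2 / 60] = √(1.5/60) = 0.158.
- SE(interaction) = √[2 × 2(1 − ρ) / 60] = √(2/60) = 0.183.

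*2c false:* women and men differ by 0.4 SD under both drugs, with the same oxytocin effect in each.
- Sex test: Φ(0.4/0.158 − 1.96) = 0.72. Range: 0.64 at ρ = 0.78 to 0.78 at ρ = 0.3.
- Interaction test: rejects at its nominal 5%.

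*2c true:* a 0.5 SD oxytocin effect in women, none in men, no placebo gap.
- Sex test: Φ(0.25/0.158 − 1.96) = 0.35.
- Interaction test: Φ(0.5/0.183 − 1.96) = 0.78. Range: 0.64 at ρ = 0.3 to 0.98 at ρ = 0.78.

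**Simulation with other placebo gaps** (4,000 runs, 60 per sex, ρ = 0.5; share of runs with p < 0.05, the drug test unpaired as in the plan):

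| Attenuation, women / men | Women minus men on placebo | 2c | Drug test | Sex test | Interaction test |
|---|---|---|---|---|---|
| 0.5 / 0.5 SD | 0 | false | 100% | 5% | 5% |
| 0.5 / 0.5 SD | +0.5 SD | false | 99% | 88% | 4% |
| 1.0 / 0 SD | +0.5 SD | true | 99% | 5% | 100% |
| 0.75 / 0.25 SD | +0.25 SD | true | 100% | 5% | 77% |

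In the last two rows the placebo gap cancels half the interaction exactly, so the sex test shows nothing although 2c is true. With 1.0 SD in women only and no placebo gap, its power would be Φ(0.5/0.158 − 1.96) = 0.89. Its result follows the placebo gap as much as the drug.

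**What the right test could detect.** With 80% power, uncorrected: (1.96 + 0.84) × √(2/60) = 0.51 SD of the within-person drug difference. In single-scan SD units this is 0.61, 0.51 and 0.40 for ρ of 0.3, 0.5 and 0.7.

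**The case against.** **2c is labelled exploratory.** No confirmatory conclusion rests on it; 2a and 2b are the main hypotheses of Aim 2. This stands and limits the weight of the point. A stated hypothesis still needs a test that matches it.

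**A general linear model can hold an interaction contrast.** The text is brief and does not rule one out. But it names exactly two differences, and the same section writes out the interaction for Aim 1 when it means one. If an interaction was intended here, one sentence would settle it.

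**The plan never says the sex map will be offered as evidence for 2c.** That is fair. The 72% is the power to detect a real sex gap and is not an error rate of the plan. It becomes an error only if the result is read as an answer to 2c.

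**The percentages depend on chosen inputs and on a threshold that is not the plan's.** Also fair. C.2.d requires correction for multiple comparisons. At the voxelwise z = 3.09 used for the pilot map (C.1.c, Figure 2), replacing 1.96 by 3.09 in the formulas above turns 72%, 35% and 78% into about 29%, 7% and 36%. Sixty per sex is also a ceiling, since scans are excluded for motion and a difference map needs both scans. These points lower every figure, but they do not turn a main effect into an interaction.

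**Conclusion.** The concern holds. Followed as written, the imaging analysis does not test 2c. This is a mismatch between a stated hypothesis and its stated test, and the orthogonality argument for it needs no assumed number.

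The percentages only illustrate how far the sex test can mislead. They rest on 60 usable pairs of scans per sex, assumed effect sizes and correlation, and an uncorrected 5% level. Because 2c is exploratory, the change is one the sponsor should make, but the trial's main conclusions do not depend on it.

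**What to change.** In the Aim 2 part of C.2.d, add the test of 2c:

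- Form each participant's oxytocin-minus-placebo map of the cocaine-minus-neutral contrast.
- Compare women with men on that map in a two-sample random-effects test, with session order as a covariate and the section's multiple-comparison correction. A sex-by-treatment contrast in a flexible factorial model is equivalent, provided that model also accounts for session.
- Report the women-versus-men main effect separately, as background on cue reactivity and not as evidence for 2c.
- State that 2c remains exploratory, and give the detectable effect at the threshold that will be used.

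While the paragraph is open, the drug comparison for 2b should also use the pairing: every participant has both scans, and an independent-samples test ignores that. The same difference maps serve both hypotheses.

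The cost is one more second-level contrast on data already being collected and a few sentences in the plan, with no added visits, scans or participants. It is best written before unblinding, so that a positive 2c result does not look post hoc.
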